10. GENERAL PRESENTATION OF SUMMARIES AND ANALYSES

10.1 Significance level

Unless otherwise specified, all statistical tests will be 2-sided hypothesis tests performed at the 5% level of

significance and all confidence intervals will be 2-sided 95% confidence intervals.

10.2 Summary Statistics

Summary statistics for continuous variables/endpoints will be presented with number of observations (n), mean, standard deviation (SD), median, minimum (min), and maximum (max). Summary statistics for categorical variables/endpoints will be presented with counts (n) and percents. Unless otherwise specified, denominator of percentage is number of subjects included in the analysis set by each group.

10.3 Decimals

Mean, standard deviation, median, minimum, maximum for descriptive statistics of continuous data, and percentage for categorical data will be presented down to 2 decimal places. P-values will be reported to 4 decimal places. If the calculated p-value is below 0.0001, it will be presented as '<0.0001'.

Results for clinical laboratory tests and vital signs will be presented to significant digits, in other words, rounded to the maximum decimal places for each item.

10.4 Statistical Analysis Methods

For a between-group comparison of categorical data, a chi-square test will be basically used and when more than 20% of the table cells have expected frequencies that are less than 5, Fisher's exact test will be presented. For confidence intervals of proportion of categorical data, if more than 20% of the table cells have expected frequencies that are less than 5, then exact 95% CIs will be calculated, otherwise approximate 95% CIs will be calculated.

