### **3) Phase III clinical study in patients with advanced or metastatic gastric cancer**

A multicenter, randomized, double-blind, phase III study was conducted in patients who failed to second-line therapy. The study was designed as 28 days/cycle, consisting of YN968D1 850 mg (as apatinib mesylate) group and Placebo group. The primary efficacy endpoint was overall survival. Randomization was done centrally and was stratified by the number of metastatic sites ( $\leq 2$  or  $> 2$ ). A total of 267 randomly assigned subjects were included in FAS population; 176 in the YN968D1 group and 91 in the Placebo group. As for the efficacy, mean overall survival was statistically greater for the YN968D1 group than for the Placebo group (6.5 months versus 4.7 months; HR= 0.709; 95% CI (0.537~0.937);  $p < 0.0149$ ). mPFS also showed the same result (2.6 months versus 1.8 months; HR= 0.444, 95%CI (0.331~0.595),  $P < 0.001$ ). ORR was 2.84% and 0.00% for the YN968D1 group and the Placebo group, respectively. As for the safety, YN968D1 was mostly controlled by treatment discontinuation or reduction. The most common adverse events were hand-foot skin reaction (HFSR), proteinuria and hypertension. In conclusion, the efficacy and safety of YN968D1 850 mg were confirmed in advanced and metastatic gastric cancer.

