7.5.3 Key Secondary Efficacy Analysis

The key secondary efficacy endpoints (PFS, ORR) will be analyzed using ITT, FAS and PPS. The key secondary efficacy analyses will be conducted using the ITT set.

- Progression Free Survival (PFS): Time from randomization to either documented radiological progression (determined by the central imaging analysis facility) or death from any cause. Subjects alive and free of progression are censored at the last tumor assessment date when alive and free of progression were known.
- Objective Response Rate (ORR): Percentage of subjects with a Best Overall Response (determined by the central imaging analysis facility) of Complete Response (CR) or Partial Response (PR).

PFS will be analyzed using the same statistical methods that are used in the primary efficacy analysis of OS.

ORR will be analyzed using the Cochran-Mantel-Haenszel test stratified by the randomization stratification factors Geographic region (Asia vs. North America/Europe), Prior ramucirumab treatment (Yes vs. No), and Treatment therapy line (3rd vs. ≥ 4th). For the ORR, the frequency and percentage (with 95% CI) of subjects will also be provided.

Data will be summarized in the following tables and figures.

-Table. Progression Free Survival [Independent Central Review] – ITT

-Table. Progression Free Survival [Independent Central Review] – FAS

-Table. Progression Free Survival [Independent Central Review] – PPS

-Figure. Kaplan Meier Plot for Progression Free Survival [Independent Central Review] - ITT

-Figure. Kaplan Meier Plot for Progression Free Survival [Independent Central Review] - FAS

-Figure. Kaplan Meier Plot for Progression Free Survival [Independent Central Review] – PPS

-Table. Objective Response Rate [Independent Central Review] – ITT

-Table. Objective Response Rate [Independent Central Review] – FAS

-Table. Objective Response Rate [Independent Central Review] – PPS

-Table. Progression Free Survival - [Investigator Review] – ITT

-Table. Progression Free Survival - [Investigator Review] – FAS

-Table. Progression Free Survival - [Investigator Review] – PPS

-Table. Objective Response Rate - [Investigator Review] – ITT

-Table. Objective Response Rate - [Investigator Review] – FAS

-Table. Objective Response Rate - [Investigator Review] – PPS

- List. Time to Event Parameters by Subjects – ITT Set

- List. Objective Response by Subject – ITT Set

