8.2.1 Overall Summary of Adverse Events

The number of subjects, incidence rate with its 95% CI and number of events will be presented for TEAEs, adverse drug reaction (ADR) and serious adverse event by treatment group during the study. Chi-square test or Fisher's exact test will be used for comparison of AE incidence between groups.

Data will be summarized in the following tables.

- *Table. Overall Summary of TEAEs – Safety Set*

- *Table. Overall Summary of Serious TEAEs – Safety Set*

- *Table. Overall Summary of ADRs – Safety Set*

- *Table. Overall Summary of Serious ADRs – Safety Set*

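### SAP 10.4 lets the pooled event count of both arms, not the count in the arm being estimated, decide whether a single-arm proportion gets an exact or an unnamed approximate 95% CI

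*SAP*

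**What the plan says.** SAP 10.4 uses one trigger twice. For between-group comparisons the default is chi-square, and "when more than 20% of the table cells have expected frequencies that are less than 5, Fisher's exact test will be presented". For the CI of a proportion, the trigger is again whether over a fifth of the cells have an expected count "less than 5, then exact 95% CIs will be calculated, otherwise approximate 95% CIs will be calculated". No approximate formula is named, the table is not defined in the CI sentence, and the SAS code in SAP section 14 is redacted. SAP 10.1 adds only that "all confidence intervals will be 2-sided 95% confidence intervals".

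Per-arm CIs for proportions are called for in three places, none of which names a method, so 10.4 governs:

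- SAP 7.5.3: "For the ORR, the frequency and percentage (with 95% CI) of subjects will also be provided".
- SAP 7.5.4: DCR, handled by the same method as ORR.
- SAP 8.2.1: "incidence rate with its 95% CI and number of events will be presented for TEAEs", and likewise for adverse drug reactions and serious events, by treatment group.

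**The concern.** The 20%-of-cells rule judges whether the chi-square approximation is adequate for a contingency table. Its expected counts come from the margins, so in a two-arm table they depend on the pooled number of events. Whether a normal approximation is adequate for one arm's proportion depends on the events and non-events in that arm. Applied to a single-arm CI, the rule can send an arm with no events to the approximate interval because the other arm had many.

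At stake is the reporting of low counts on placebo (few or no responders, few serious drug reactions) and of near-universal events on the active arm. Under one common approximation these could appear with impossible limits or with no apparent uncertainty.

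**Working it through.** The SAP gives no numerical result for this rule, so there is no figure of its own to reproduce.

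**Inputs.** About 459 subjects (Protocol synopsis) randomized 2:1 (SAP 3.4), taken as 306 active and 153 placebo. Two-sided 95% CIs (SAP 10.1). Earlier trials (Protocol 1.2): in phase III, "ORR was 2.84% and 0.00% for the YN968D1 group and the Placebo group, respectively"; in phase II, nine partial responses, all in the two active groups, among 144 patients randomized to three groups. Assuming equal groups, 96 of those were on active treatment.

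**Step 1: where the rule switches.** In a 2x2 table one cell is 25% of the cells, so a single expected count below 5 triggers the exact interval. With T pooled events the smallest expected event cell is T x 153/459 = T/3.

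- T = 14: 4.67, below 5, exact.
- T = 15: 5.00, not below 5, approximate.

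The switch is at 15 for any exact 2:1 split; at 307:152 it is at 16. So placebo 0/153 gets an exact CI if the active arm has 14 events and an approximate one if it has 15, although the placebo data are identical.

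**Step 2: the intervals.** Wald is p ± 1.96 x sqrt(p(1-p)/n). For placebo, n = 153:

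| Events | Wald | Wilson | Clopper-Pearson |
|---|---|---|---|
| 0 | 0.00 to 0.00% | 0.00 to 2.45% | 0.00 to 2.38% |
| 1 | -0.62 to 1.93% | 0.12 to 3.61% | 0.02 to 3.59% |
| 2 | -0.49 to 3.11% | 0.36 to 4.64% | 0.16 to 4.64% |
| 3 | -0.24 to 4.16% | 0.67 to 5.61% | 0.41 to 5.62% |
| 4 | 0.09 to 5.14% | 1.02 to 6.53% | 0.72 to 6.56% |

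At the other end, 303/306 has a Wald upper limit of 100.1% (exact 99.8%). The rule allows this when placebo has at least 12 non-events, making 15 non-events in total.

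**Step 3: coverage of the placebo CI under the rule.** Exact binomial enumeration over both arms, with Clopper-Pearson when the rule calls for exact and the stated approximation otherwise. The true rates are illustrative assumptions; the documents do not give them.

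| True rates, active v placebo | Approximate = Wald | Approximate = Wilson |
|---|---|---|
| 5% v 0.5% | 73.5% | 96.3% |
| 6% v 1% | 82.2% | 93.3% |
| 15% v 2% | 80.9% | 96.5% |
| 10% v 3% | 93.9% | 94.9% |
| 30% v 5% | 94.0% | 94.0% |

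Clopper-Pearson throughout gives about 98 to 99% at the first three points.

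**Step 4: would ORR reach the switch?** With no placebo responders, 15 active responders are needed.

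- Phase III rate: 0.0284 x 306 = 8.7 expected; the binomial probability of 15 or more is about 3%.
- Phase II rate: 9/96 x 306 = 28.7 expected; the probability is above 99%.

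**The case against.** **The formula.** A reader might infer that the SAP prescribes Wald intervals. It does not: it says only approximate, and the code that might settle it is redacted. Step 3 shows that the undercoverage depends almost wholly on that choice. This objection stands, so every Wald figure here is conditional. It does not remove the dependence of the method on the other arm's data.

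**The table.** The CI sentence does not say that the table is arm by outcome. If it meant the event and non-event counts of the one arm, 0 to 4 events in 153 would leave one of two cells below 5 and give the exact interval; Wald coverage at the first three points would then be 99.3%, 99.9% and 99.6%. The reading is possible. The two-arm reading is more natural, because the preceding sentence uses the same wording for a between-group comparison, but the text does not settle it.

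**The reach.** A reader might also infer that CIs for rare individual events are affected. SAP 8.2.2 and 8.2.3 ask for incidences, counts and percentages by system organ class and preferred term, without CIs. Nor do the documents support a forecast that placebo ORR will be reported with zero width: at the earlier phase III rate the exact branch would almost always apply.

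**The consequence.** ORR is tested by stratified Cochran-Mantel-Haenszel, adverse-event incidence by chi-square or Fisher, and futility by conditional power for OS. None uses these CIs. This stands and keeps the severity low.

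**Conclusion.** The point holds as a low-severity flaw in specification, with medium confidence. On the natural two-arm reading, at 2:1 allocation, the CI method for one arm turns on 15 pooled events rather than on that arm's own count. That is a poor rule whichever approximation is meant.

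The size of the harm rests on two assumptions: that the table is arm by outcome, and that approximate means Wald. Under both, zero events give an interval of no width, one to three events give a negative lower limit, and placebo coverage is about 74 to 82% at true placebo rates of 0.5 to 2%. The loss is slight at 3 to 5%. With Wilson it largely disappears.

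The effect is confined to the descriptive per-arm CIs for ORR, DCR and the overall adverse-event summaries. For ORR it depends on the response rate: unlikely at the earlier phase III rate, near certain at the phase II rate.

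**What to change.** In SAP 10.4, replace the CI sentence with one that names a single interval valid at small counts for every per-arm proportion (ORR, DCR and adverse-event incidence), whatever the pooled expected counts. Clopper-Pearson and Wilson both serve. Keep the cell rule only for choosing between chi-square and Fisher tests.

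The cost is one sentence in the SAP and a matching check of the section 14 code. Clopper-Pearson gives slightly wider, conservative intervals; Wilson is closer to nominal on average but can fall a little below 95%. No hypothesis test, sample size or stopping rule changes.

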10.5 Baseline

Baseline is defined as the value at Cycle 1 Day 1, or the last value observed prior to randomization if this is not available.

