The overall mean pharmacokinetic parameters of YN968D1 after single and multiple oral dose administration are summarized in Table 3 below. For single dose evaluation,  $C_{max}$  was achieved in 3 to 4 hours after oral administration. The plasma level of YN968D1 varied considerably between patients. The concentration of YN968D1 in plasma increased with dose.  $C_{max}$  and  $AUC_{0-24}$  showed a dose-dependent increase at doses from 500 to 850 mg, whereas increased slightly more than dose proportionally at dose of 850 mg dose, and showed high inter-individual variability. The elimination half-life of the terminal phase ( $t_{1/2\lambda_z}$ ), estimated to be approximately 9 hours, was consistent over the three dose levels.

For multiple-dose at 750 mg, the mean  $C_{max}$  was 2,421 ng/mL on Day 1, which increased to 2,553 ng/mL by Day 6, and the mean  $AUC_{0-24}$  was 19,399 ng·h/mL on Day 1, which increased to 25,449 ng·h/mL by Day 6. There was no further increase in  $C_{max}$  and  $AUC$  beyond 6 days of multiple dosing, and this was similar for the mean elimination  $t_{1/2}$ . Steady-state conditions were achieved by Day 6, suggesting no accumulation during 56 days of once-daily dosing.

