### 3.4.2. Baseline Visit (Day 1 in Cycle 1)

Randomized subjects will receive the assigned investigational product as instructed. The following procedures are carried out at this visit.

- Physical examination
- Measurement of vital signs including weight
- Assessment of ECOG performance score
- 12-lead ECG (Before IP administration)
- Chest X-ray, pregnancy test (serum or urine), biopsy
- Collection of concomitant medication information
- Randomization
- Completion of patient reported outcome (EORTC QLQ-C30, EORTC QLQ-STO22, EQ-5D-5L)

- Pharmacodynamic (PD) marker test
- Dispense of investigational product
- Administration of investigational product
- Blood sampling for Cycle 1 Day 1 PK
- 12-lead ECG (Approximately 4 hours after IP administration and corresponding to PK sampling)
- Assessment of adverse events

 Only done when clinically indicated. The following countries require a pregnancy test at the beginning of each treatment cycle for the applicable subjects: Germany, Romania, and Poland.

If a randomized subject is found not to meet any of the eligibility criteria before the first administration of the investigational product, the subject will not be started on the study treatment and will be withdrawn from the study. Subjects who are randomized but never receive the investigational product or subjects who are withdrawn from the study before randomization will not be allowed to re-consent.

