### 5.3.6. ECG Monitoring

A 12-lead ECG should be performed within 14 days before the date of randomization, at Day 1 of every cycle (before IP administration), at EOT visit and at the post-treatment follow-up visit. In addition, a 12-lead ECG should be performed approximately 4 hours after IP administration on Cycle 1 Day 1 and Cycle 1 Day 15. Additional ECG should be performed as clinically indicated. Any abnormal findings in ECG measurements with clinical significance should be reported as adverse events.

To facilitate the safety analysis in [section 8.3.7](#) of the ECG data, if approved by country and local regulatory authorities, duplicate copies (either digital or hard copies) of the ECG tracing and the evaluation report should be transferred to the Sponsor after de-identifying the subject information for further clinical evaluation of ECG data as per regulatory recommendations. The original ECG results will be kept on file at the site as source documentation. Handling of this information/data will be done in accordance with the applicable data protection laws. (US government CFR 21 Part 11 for electronic records; US government Health Insurance Portability and Accountability Act (HIPPA), etc.)

As the request for the ECG copies is during an amendment, it is typically necessary to either ensure that informed consent is obtained to facilitate submittal of these ECG copies to the sponsor (or sponsor representatives) or in the case where consent cannot be updated (i.e. subject has expired), appropriate local ethics committee approval is obtained to authorize the submittal of these ECG copies.

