5.9.6 Vital Signs

Systolic blood pressure, diastolic blood pressure, pulse, body temperature, respiratory rate, weight, height and BMI will be collected. Weight (kg) will be measured at each visit and height (cm) will be measured only at the screening visit.

5.9.7 12-Lead Electrocardiogram (ECG)

Heart rate, PR interval, QTcF, RR interval, ST segment, T-wave, Heart rate, and whether the result is normal/abnormal and clinically significant/not-significant will be collected. For Day 1 of Cycle 1 and 2, 12-lead ECG will be collected before the IP administration and approximately 4 hours after IP administration which corresponds to the time when the PK C_{max} blood is drawn.

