8.5.2 Physical Examination

Subjects with at least once clinically significant abnormal result at all time points after first IP administration on physical examination will be summarized by treatment group. Clinically significant result of physical examination will be listed.

Data will be summarized in the following table and list.

- *Table. Clinically Significant Physical Examination – Safety Set*
- *List. Subjects with Clinically Significant Abnormal on Physical Examination – Safety Set*

8.5.3 12-lead Electrocardiogram

Values for ECG parameters (Heart rate, PR interval, QTcF and RR Interval) and the change from baseline will be summarized with descriptive statistics by time point and treatment group. The ECG result will be presented in shift tables (Normal, Abnormal NCS, or Abnormal CS) from baseline to each scheduled time point by time point and treatment group. Significant shift from baseline will be tested using McNemar's test.

Data will be summarized in the following tables and list.

- *Table. 12-lead Electrocardiogram [Parameter] – Safety Set*
- *Table. Shift from baseline on 12-lead ECG – Safety Set*
- *List. Subjects Shifting from Normal or NCS at baseline to CS at Post-Treatment on 12-lead ECG – Safety Set*

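### SAP 10.5 does not require the baseline ECG to be predose, so where the Cycle 1 Day 1 predose tracing is missing the rule takes the 4-hour post-dose tracing as baseline

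*SAP*

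**What the plan says.** The SAP has a single baseline definition, in section 10.5: "Baseline is defined as the value at Cycle 1 Day 1, or the last value observed prior to randomization if this is not available". It is tied to a visit, not to the time of first dose, and it has no separate rule for ECG.

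The Cycle 1 Day 1 visit has two ECGs. SAP 5.9.7 states: "For Day 1 of Cycle 1 and 2, 12-lead ECG will be collected before the IP administration and approximately 4 hours after IP administration". Protocol 5.3.6 schedules a predose ECG on Day 1 of every cycle and adds that "a 12-lead ECG should be performed approximately 4 hours after IP administration on Cycle 1 Day 1 and Cycle 1 Day 15". Protocol 3.4.2, which describes the visit called Baseline, lists both tracings. Note 20 to protocol Table 1 ties the 4-hour tracing to the Cmax sample, and protocol 1.2 reports that in phase I the peak "was achieved in 3 to 4 hours after oral administration". A drug-free screening ECG is also scheduled, within 14 days before randomization.

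The baseline feeds SAP 8.5.3: "Values for ECG parameters (Heart rate, PR interval, QTcF and RR Interval) and the change from baseline will be summarized". The same section plans shift tables (normal, abnormal not clinically significant, abnormal clinically significant) and a listing of subjects who move to clinically significant.

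**The concern.** A rule that picks the value at a visit works only if the visit yields one value, or if all its values are drug-free. For ECG neither holds. The fallback to a pre-randomization value opens only when no Cycle 1 Day 1 value is available. A subject with a missing predose tracing and a recorded post-dose tracing does have one, so the literal rule selects an on-drug ECG although a drug-free one is on file.

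A post-dose baseline can carry drug effect only in the apatinib arm. If apatinib prolongs QTcF in step with concentration, subtracting such a baseline removes much of the effect from that arm's change scores and leaves placebo untouched. A subject whose 4-hour tracing is already clinically significant would start in that category, and so could not appear in the listing of subjects shifting into it. The protocol treats QT as a live question: it has QTcF exclusion limits, restricts QT-prolonging drugs, and asks for ECG copies for further evaluation.

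**Working it through.** The plan states no QTcF effect, standard deviation or threshold for change, so there is no figure to reproduce. The check is of the text, followed by an illustration.

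**1. What the rule selects in each case (ECG)**

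| Predose Day 1 | 4 h post-dose Day 1 | Screening | SAP 10.5 read literally |
|---|---|---|---|
| present | missing | present | predose: correct |
| missing | missing | present | screening: correct |
| missing | present | present | post-dose: on drug |
| present | present | present | not determined by 10.5 |

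The third row is a wrong result from the rule as written. The fourth is an ambiguity.

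**2. Whether another section closes the gap**

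SAP 5.9.7 and 8.5.3 do not define an ECG baseline. SAP 5.2 does state that the baseline sample precedes the first dose, but only for the pharmacodynamic markers.

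**3. Direction and possible size (illustration only)**

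Assumptions, none of them in the documents: the QTcF effect is proportional to concentration at the time of the tracing, and equals E = 10 ms at the mean Day 1 peak.

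Inputs from protocol Table 3 (750 mg mesylate, n = 11): mean Cmax 2,421 ng/mL on Day 1, 2,553 on Day 6 and 2,210 on Day 28. Half-lives across the table run from 8.1 to 11.3 h.

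The only later near-peak ECG in protocol 5.3.6 is on Cycle 1 Day 15. Table 3 has no Day 15 value, so Days 6 and 28 are used to bracket it.

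- Change from a predose baseline = E × C / 2,421. Day 6: 10 × 2,553 / 2,421 = 10.5 ms. Day 28: 10 × 2,210 / 2,421 = 9.1 ms.
- Change from a post-dose baseline = E × (C − 2,421) / 2,421. Day 6: 10 × 132 / 2,421 = +0.5 ms. Day 28: 10 × (−211) / 2,421 = −0.9 ms.

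The other on-treatment ECGs in the protocol are predose on Day 1 of later cycles, about 20 h after the previous dose's 4-hour point. The fraction of peak remaining is 2^(−20 / half-life): 0.181 at 8.1 h and 0.293 at 11.3 h.

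- From a predose baseline: 9.13 × 0.181 to 9.13 × 0.293, about 1.6 to 2.7 ms.
- From a post-dose baseline: the same minus 10, about −8.4 to −7.3 ms, an apparent shortening.

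**4. Effect on the arm mean**

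If a fraction f of apatinib subjects at a time point have a post-dose baseline, the mean change falls by f × E. With E = 10 ms, each 1% affected costs 0.01 × 10 = 0.1 ms.

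**5. A related mismatch**

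SAP 5.9.7 puts the post-dose ECGs on Day 1 of Cycles 1 and 2. Protocol 5.3.6 and Table 1 note 20 put them on Days 1 and 15 of Cycle 1. SAP 5.9.7 says that its post-dose ECGs match a Cmax draw, yet the sampling table in protocol 5.4.4 has only a predose sample on Cycle 2 Day 1.

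**The case against.** The best reply is that the predose tracing is plainly intended. Protocol Table 1 marks the baseline-column ECG as a procedure done before dosing. Protocol 5.3.6 and note 20 treat the predose ECG as routine and the 4-hour one as additional. SAP 8.5.3 summarizes ECG by time point, whereas vital signs and ECOG are summarized by visit, which suggests that the two Day 1 tracings are separate points. This stands where both tracings exist, and it makes misuse there unlikely. It does not help where the predose tracing is missing, because 10.5 then points to the wrong value. The mock-up tables named in the SAP appendix might settle the labelling, but they are not reproduced and cannot be checked.

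It is also fair that SAP 8.5.3 summarizes QTcF values as well as changes, that clinically significant ECG findings are reported as adverse events, and that tracings go to the sponsor where approved. None of these depends on baseline, so the wording would not conceal a prolongation signal altogether.

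A reader might also infer that the fallback in 10.5 loses values taken after randomization but before first dose. The schedule does not support that: both events belong to the Cycle 1 Day 1 visit, so such a value is already a Cycle 1 Day 1 value.

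**Conclusion.** The point holds as a gap in the baseline definition. SAP 10.5 gives a wrong ECG baseline when the predose Day 1 tracing is missing and the post-dose one is present, and it leaves the choice unstated when both are present. The affected outputs are the QTcF change summaries and ECG shift tables. The bias in affected apatinib subjects is towards no effect, or apparent shortening at trough, provided that QTcF rises with concentration. A slow-onset effect would be attenuated less.

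The number affected is not stated. It is probably small, since it needs one Day 1 tracing missing and the other recorded.

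Two stronger readings are not supported:

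- **That every subject could be affected.** This would need an analyst to prefer the post-dose tracing when a predose one exists. Nothing instructs that, and the context points the other way.
- **That about 95% of the effect is removed in each affected subject** (2,421 / 2,553 = 0.948). This is a ratio of phase I group means, with a Day 1 Cmax coefficient of variation of 68.5%. It uses Day 6, when no ECG is scheduled, and it rests on an assumed proportional effect. The figures in the working show direction and possible scale at mean concentrations, not an estimate for this trial.

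The correction is worth making because the remedy is standard and cheap.

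**What to change.** In SAP 10.5, define baseline as the last non-missing value before the first dose of study drug. For ECG, add that this is the Cycle 1 Day 1 predose tracing or, if that is missing, the screening ECG, and that the Cycle 1 Day 1 post-dose tracing is always a post-baseline time point. For randomized subjects who are never dosed, who enter ITT summaries but not the Safety Set, keep a fallback to the last value up to randomization.

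Reconcile SAP 5.9.7 with protocol 5.3.6 and Table 1 note 20 on the days of the post-dose ECGs, so that the planned time points match the data collected.

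The cost is a few sentences in the SAP and a check that the ECG derivation separates the two Day 1 tracings by time relative to first dose. No data collection changes. The edit should be made before unblinding.
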